Evaluation of the Treatment of Multiple Gingival Recession Using Modified Coronally Advanced Tunnel With Subepithelial Connective Tissue Graft Depending on the Positioning of the Graft

NCT06366022

04/10/2024

Current State of Knowledge

Thanks to the modified tunnel technique using an autogenous subepithelial connective tissue graft, we can effectively treat gingival recessions. [1] This surgical approach ensures minimal postoperative discomfort for patients, among other reasons due to minimizing vertical incisions and preserving the integrity of the interdental papilla. The material considered the gold standard in root coverage procedures is an autogenous connective tissue graft. [2] One method of harvesting it is de-epithelialization of a free gingival graft (FGG).

Purpose of the study

The aim of the present study is to compare the outcomes of a modified tunnel technique with an autogenous subepithelial connective tissue graft in gingival recessions, depending on whether the graft is positioned with its inner surface (previously adjacent to the periosteum) facing the covering flap versus its outer surface facing the covering flap.

Description of the study

- **Type of study:** randomized split-mouth interventional study.
- **Sample size:** 20 test sites and 20 control sites (20 patients)
 - a. **Inclusion criteria:**
 - I. Adult patients aged 18 to 60 years
 - II. Generally healthy patients or patients with controlled systemic diseases
 - III. Presence of multiple gingival recessions
 - b. **Exclusion criteria:**
 - I. Plaque index $\geq 20\%$ (Ainamo & Bay 1975)
 - II. Bleeding index $\geq 15\%$ (Mühlemann & Son 1971)
 - III. Tobacco smoking
 - IV. Uncontrolled systemic diseases with potential impact on tissue healing
 - V. Use of medications affecting healing (cytostatics, corticosteroids)
 - VI. Pregnant or breastfeeding women
- **Study endpoints:**

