 - I. **Primary endpoint** – gingival recession/root coverage.
 - II. **Secondary endpoints** – gingival thickness, width of keratinized gingiva.

- **Procedure description:**

After obtaining written informed consent, the following periodontal parameters will be assessed: probing depth, height and width of gingival recession, gingival thickness (1 mm from the gingival margin), and width of keratinized gingiva. Then, under local anesthesia, root coverage surgery will be performed using a modified tunnel technique with an autogenous subepithelial connective tissue graft (sCTG). On the test side, the graft will be positioned with its inner surface (previously adjacent to the periosteum) facing the flap covering the graft, whereas on the control side the graft will be positioned with its outer surface facing the flap covering the graft. (Allocation of test and control sides will be determined by coin toss: heads = left side, tails = right side). After surgery, the patient will receive questionnaires assessing postoperative discomfort, separately for each operated side. Follow-up visits will be scheduled at 1 week and 2 weeks after the procedure. Measurements of the listed gingival parameters will be performed at 6 and 12 months postoperatively. Additionally, 12 months after surgery, a gingival biopsy (2.5 mm in diameter and 1 mm thick) will be collected for histological analysis.

Statistical analysis plan

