The results will be presented using descriptive statistics such as means, standard deviations (SD), percentages, and frequencies. Baseline defect characteristics will be used to ensure test and control sides were similar. The analyzed metrics will be calculated as follows: (1) MRC = $\frac{GR_0 - GR_6}{GR_0} \times 100\%$ (after 6 months); MRC = $\frac{GR_0 - GR_{12}}{GR_0} \times 100\%$ (after 12 months), (2) recession reduction (GR red) = $GR_0 - GR_6$ (after 6 months); GR red = $GR_0 - GR_{12}$ (after 12 months), (3) CAL gain = $CAL_0 - CAL_6$ (after 6 months); CAL gain = $CAL_0 - CAL_{12}$ (after 12 months), (4) KTW gain = $KTW_6 - KTW_0$ (after 6 months); KTW gain = $KTW_{12} - KTW_0$ (after 12 months), and (5) GT gain = $GT_6 - GT_0$ (after 6 months); GT gain = $GT_{12} - GT_0$ (after 12 months). The normality of distribution of quantitative variables will be verified with the Shapiro–Wilk test. The primary outcome variable (MRC) will be tested for superiority by Student’s t-test. The secondary outcomes will be tested for side differences by Student’s t-test. If significant, the outcomes will be verified by repeated measures of variance, with subject as random effect used ANOVA approach. Pearson’s chi-squared test will be used for comparison of fractions and the agreement of variable class distribution between tests and controls. Statistical significance will be defined as p value < 0.05.

Benefits of the study

It is anticipated that the side on which the sCTG is positioned during the tunnel technique procedure will not affect the surgical outcome.

Risks of taking part in the study

Surgical treatment may cause pain, swelling, and bruising/hematomas of the gingiva and facial skin.

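### The only analysis with a patient effect is run only after a significant t-test that is not stated to be paired, so a null result may come from the screen and the verification step adds little or nothing

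*Combined protocol and SAP*

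**What the plan says.** Description of the study calls the trial a "randomized split-mouth interventional study" with "20 test sites and 20 control sites (20 patients"). An inclusion criterion is "Presence of multiple gingival recessions"; the number of treated teeth per side is not given. Under Procedure description, "Measurements of the listed gingival parameters will be performed at 6 and 12 months postoperatively".

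The Statistical analysis plan defines each outcome separately at 6 and at 12 months and names no primary time point. It then gives three sentences in sequence:

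- On root coverage, it states: "The primary outcome variable (MRC) will be tested for superiority by Student’s t-test".
- On gingival thickness, keratinized width and the rest, it states: "The secondary outcomes will be tested for side differences by Student’s t-test".
- On what happens after a positive test, it states: "If significant, the outcomes will be verified by repeated measures of variance, with subject as random effect used ANOVA approach".

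It does not say whether either t-test is paired, whether the unit is the tooth, the side or the patient, or how the two visits enter the repeated-measures model. Subject is the only random effect named. No model follows a non-significant t-test. Benefits of the study states the expectation that graft orientation makes no difference to the result.

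**The concern.** In a split-mouth trial the gain in precision comes from comparing two sides of the same mouth. The plan acknowledges that dependence only in the second step, and that step is conditional on significance. An outcome that misses the first test may never receive the analysis that suits the design. Because no difference is expected, the likely result falls in the branch that is never re-examined.

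The second step is also called a verification. A reader of the trial report would take a verified result as stronger evidence than a single p-value. Whether it is stronger depends on choices the plan leaves open.

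**Working it through.** **Inputs.** From the documents: n = 20 pairs, visits at 6 and 12 months, significance at 0.05. Assumed: two-sided testing, normal outcomes, between-side correlation ρ, and persistence k, the share of within-patient variance that belongs to a side and stays with it across visits. The plan gives no power, effect size or SD, so it has no figure to reproduce.

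**Reading A: the t-test is unpaired.**
1. With 20 pairs, a paired t-test has 80% power at a true difference of 0.66 SD of the paired difference (noncentral t).
2. In units of the outcome SD, that difference is δ = 0.66 × √(2(1−ρ)).
3. The unpaired statistic is centred near δ/√(2/20) = δ/0.316. Its true spread is about √(1−ρ), but it is compared with 2.024 (t, 38 df) as though the spread were 1.

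| ρ | δ | centre | spread | power, normal approximation | power, simulated | type I error, simulated |
|---|---|---|---|---|---|---|
| 0.3 | 0.781 | 2.469 | 0.837 | 70% | 70% | 2.1% |
| 0.5 | 0.660 | 2.087 | 0.707 | 54% | 54% | 0.7% |
| 0.7 | 0.511 | 1.617 | 0.548 | 23% | 26% | 0.1% |

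Example at ρ = 0.5: (2.024 − 2.087)/0.707 = −0.09, so power is about 54%. At ρ = 0 nothing is lost.

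A second illustration uses a difference of 0.5 SD with ρ = 0.5. The unpaired test is significant in 28.5% of trials and the subject-effect ANOVA in 56.4%. About (56.4 − 28.5)/56.4 = 49% of the ANOVA's positives would never be reached.

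**Reading B: the t-test is paired, one value per side.** Let d be the within-patient difference. In an ANOVA with side and subject, the side sum of squares is n·d̄²/2 on 1 df and the residual mean square is s_d²/2. Hence F = n·d̄²/s_d² = t². A generated data set of 20 pairs confirms it: F = t² = 0.0929, p = 0.764 by both. Every positive is confirmed because the test is the same.

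**Reading C: both visits enter, with subject as the sole random effect.** In units of within-patient variance, the correct error mean square for the side contrast (side by subject, 19 df) is 1 + k. The subject-only model pools it with 38 df of mean square 1 − k: [19(1+k) + 38(1−k)]/57 = 1 − k/3. The variance is understated by the factor (1+k)/(1−k/3).

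| k | variance factor | model's own type I error | false positives of a paired 12-month t-test that it confirms | both tests positive under the null |
|---|---|---|---|---|
| 0.3 | 1.3/0.900 = 1.44 | 10% | 61% | 5% × 0.61 = 3.1% |
| 0.5 | 1.5/0.833 = 1.80 | 14% | 81% | 5% × 0.81 = 4.1% |
| 0.7 | 1.7/0.767 = 2.22 | 19% | 94% | 5% × 0.94 = 4.7% |
| 0.9 | 1.9/0.700 = 2.71 | 24% | 100% | 5% × 1.00 = 5.0% |

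The error and confirmation rates are simulated. A side-level analysis of the same data holds 5%. Entering 2 to 4 teeth per side instead of two visits has a similar effect: type I error of 7 to 33% for the subject-only model when side within subject carries 0.1 to 0.5 of the variance.

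**The case against.** A reader might infer from Reading C that the plan has a false-positive rate of 10 to 24%. It does not. That is the error of the pooled model run on its own. Under the quoted rule a verified result needs both tests positive, so its rate cannot exceed that of the t-test. With a paired first test the table gives 3.1 to 5.0%.

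A reader might also infer that the plan specifies a model with subject as the only random effect and both visits entered. The text names subject but never says only, and it defines every outcome by visit. With one value per side a subject effect is sufficient, and the step is redundant rather than anti-conservative. Even with both visits, a classical repeated-measures ANOVA that tests side against side-by-subject holds about 5%. The wording neither states nor excludes that.

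Nor does the step confirm almost any positive on every reading. At k = 0.1 it confirms about 41% of false positives.

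The power loss, for its part, requires an unpaired test. Student's t-test can mean the paired form, and in that case every outcome already receives a suitable analysis. Finally, the conditional sentence follows the one on secondary outcomes, so it may not govern MRC.

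These points limit the size and reach of the problem. They do not remove the condition on significance or the silence on pairing, and no reading examined makes the second step both well specified and informative.

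**Conclusion.** The concern holds as a fault of specification with a possible loss of power, not as inflation of the trial's false-positive rate. The condition on significance and the missing statement of pairing are direct readings of the Statistical analysis plan. They apply certainly to the secondary outcomes and possibly to MRC.

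If the t-test is unpaired, power falls from 80% to about 70%, 54% or 26% at ρ = 0.3, 0.5 or 0.7, and an expected null cannot be told apart from an insensitive test. If it is paired with one value per side, the verification is empty. If visits are pooled with subject as the sole random effect, it is a weak check that passes 61 to 100% of false positives at k = 0.3 to 0.9. All values of ρ and k are assumptions, as are two-sided testing and normality. The point should be settled before analysis, but it does not by itself make a positive finding unsafe beyond the nominal 5% of a paired first test.

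**What to change.** Delete the conditional verification sentence. For every outcome, MRC included, prespecify one within-patient analysis that runs whatever any earlier p-value shows:

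- Average the teeth within a side, so that each patient gives one test and one control value.
- Apply a paired t-test to the 20 test-minus-control differences at a time point named in advance as primary (6 or 12 months; the choice is the investigators').
- Report the mean difference with its 95% confidence interval, so that a null result shows what differences it excludes.

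If both visits are to be modelled together, use a linear mixed model with graft position, visit and their interaction, and random effects for patient and for side within patient. This is an alternative to the paired t-test, not an equivalent; one of the two should be named as primary.

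The cost is SAP wording. No new data or patients are needed. The downside is larger standard errors than a subject-only model pooling both visits would have shown.
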